10.5.2 EPS Scales

A participant will be considered to have treatment-emergent parkinsonism if the participant's SAS score was ≤ 3 at baseline and > 3 at any DB assessment. A participant will be considered to have treatment-emergent akathisia if the participant's BARS score was ≤ 2 at baseline and > 2 at any DB assessment. The number and percentage of participants reporting treatment-emergent parkinsonism or treatment-emergent akathisia will be tabulated by treatment group. Listings of participants with treatment-emergent parkinsonism and participants with treatment-emergent akathisia will be provided and will include the participant identification number, study center number, and baseline and postbaseline values. Listings of all AEs occurring in participants who have treatment-emergent parkinsonism or treatment-emergent akathisia will also be provided.

Descriptive statistics for EPS scale parameters (AIMS, BARS, and SAS) and changes from baseline values at each assessment timepoint in this study will be presented.

10.5.3 Suicidality Assessment

The number and percentage of patients with suicidal ideation or suicidal behavior as recorded on the C-SSRS will be summarized by treatment group. The distribution of responses for most severe suicidal ideation and most severe suicidal behavior during the patient's lifetime, during the DB treatment period, and during the safety follow-up period will also be presented by treatment group for the safety population. Supportive listings will be provided and will include the patient identification number, study center number, lifetime history, and postbaseline values. Intensity of suicidal ideation, suicidal behavior type, and lethality of suicidal behavior will also be included in these listings. A listing of all AEs occurring in patients who have suicidal ideation or suicidal behavior will also be provided.

11.0 **HEALTH OUTCOMES ANALYSES**

The SF-12 will be administered at Visit 2 and Visit 6/ET.

Analysis of change from baseline in the PCS-12 and MCS-12 score at Week 6 will be analyzed using the ANCOVA (based on observed cases) that has treatment group, pooled country, ADT failure category (per CRF) as factors and the baseline value as the covariate.

The detailed algorithms for derivation of the PCS-12 and MCS-12 score are presented in Section [15.2.1](#).

12.0 **INTERIM ANALYSIS**

No interim analysis is planned for this study.

13.0 **DETERMINATION OF SAMPLE SIZE**

The study will randomize approximately 750 participants in a 1:1:1 ratio to cariprazine 1.5mg/day, cariprazine 3mg/day, and placebo groups. A sample size of 250 participants per arm will provide approximately 83% statistical power to show statistically significantly higher effect in each dose of cariprazine versus placebo based on the mITT analysis set. The study has approximately 90% statistical power to show that at least 1 of the 2 cariprazine doses is statistically significantly more efficacious than placebo in the primary endpoint. These calculations assumed an effect size of 0.286. All statistical powers presented in this section were calculated adjusting for multiple comparisons across the two cariprazine doses and the primary and secondary endpoints using the Hochberg-based gatekeeping procedure with re-testing with the family-wise type I error rate being controlled at a 0.05 level (2-sided). The dropout rate is assumed to be 15% at Week 6. Within-person correlation for the primary endpoint is assumed to be 0.58. This value is used in the sample size calculation to calculate an inflation factor that accounts for information loss due to the missing data at Week 6 for longitudinal data collection.

Assumptions of effect size, intracorrelation and dropout rate are based on cariprazine Study RGH-MD-75.

14.0 **STATISTICAL SOFTWARE**

Statistical analyses will be performed using version 9.4 (or newer) of SAS on a Linux operating system.

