4.4 Exclusion Criteria

The following are criteria for exclusion from participating in the study:

1. Diagnosis of any current psychiatric diagnosis other than MDD (including those with current intellectual development disability) with the exception of specific phobias
2. History of manic or hypomanic episodes
3. Patients with a YMRS score ≥ 12
4. Patient has a history of meeting DSM-5 diagnosis for any substance-related disorders (ie, use disorders except caffeine- and tobacco-related) within the 3 months before Visit 1 (Screening)
5. Patient had a positive result at Visit 1 (Screening) from the urine drug screen (UDS) for any prohibited drugs. Exception: patients with a positive UDS at Visit 1 for opiates, cannabinoids, amphetamines, barbiturates, or benzodiazepines may be allowed in the study provided:
 - a. The drug was used for a legitimate medical purpose;
 - b. The drug can be discontinued prior to further participation in the study (except for benzodiazepines which may be continued if the patient has been taking a stable dose [ie, lorazepam up to 2 mg/day or its benzodiazepine equivalent] for at least 1 month prior to Visit 1 (Screening) or if used as rescue during washout); and

- c. A repeat UDS must be performed prior to Visit 2 and must be negative, except benzodiazepine use as described in 4(b) and Section 4.5.3
- 6. The patient represents a suicide risk, as determined by meeting any of the following criteria:
 - a. Patient made a suicide attempt within the past year prior to Visit 1 (Screening)
 - b. Patient had a score of 4 or greater on Item 10 of the MADRS at Visit 1 (Screening) or Visit 2 (Baseline)
 - c. Patient had a score of 3 or greater on Item 3 of the HAMD-17 at Visit 1 (Screening) or Visit 2 (Baseline)
 - d. Patient is at significant risk, as judged by the investigator, based on the psychiatric interview or information collected in the Columbia–Suicide Severity Rating Scale (C-SSRS) at Visit 1 (Screening) or Visit 2 (Baseline)
- 7. Patient is at imminent risk of injuring self or others or causing significant damage to property, as judged by the investigator
- 8. Patient has a history of intolerance or hypersensitivity to cariprazine or other drugs of the same class or to rescue medications

Treatment-Related Criteria:

- 9. Per ATRQ, patient failed to respond to > 3 trials of ADTs given at an adequate dose (as defined by the ADT package insert) and duration of ≥ 6 weeks during the present episode

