6.6.6.2 Columbia–Suicide Severity Rating Scale

The C-SSRS is a clinician-rated instrument that reports the severity of both suicidal ideation and behavior. Suicidal ideation is classified on a 5-item scale: 1 (wish to be dead), 2 (nonspecific active suicidal thoughts), 3 (active suicidal ideation with any methods [not plan] without intent to act), 4 (active suicidal ideation with some intent to act, without specific

plan), and 5 (active suicidal ideation with specific plan and intent). The C-SSRS also captures information about the intensity of ideation, specifically the frequency, duration, controllability, deterrents, and reasons for the most severe types of ideation. Suicidal behavior is classified on a 5-item scale: 0 (no suicidal behavior), 1 (preparatory acts or behavior), 2 (aborted attempt), 3 (interrupted attempt), and 4 (actual attempt). More than 1 classification can be selected provided they represent separate episodes. For actual attempts only, the actual or potential lethality is classified for the initial, most lethal, and most recent attempts. The C-SSRS will be completed at all study visits. At Visit 1 (Screening), the C-SSRS will be completed for the patient's lifetime history of suicidal ideation and behavior, including a 12-month lookback. At all other visits the C-SSRS will be completed for ideation and behavior since the previous visit.

The C-SSRS must be completed by an investigator, subinvestigator or trained rater, all of whom must have extensive professional training.

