The safety analysis will be performed using the safety population for the double-blind treatment period and safety follow-up period. The double-blind treatment period starts with the first dose of double-blind investigational product and ends with the last scheduled assessment at Visit 6 (Week 6) or early termination (before Week 6). The safety follow-up period starts the day after the last scheduled assessment at Visit 6 (or early termination) and ends with the last safety follow-up visit. The safety parameters will include adverse events (AEs), clinical laboratory parameters, vital signs, electrocardiogram (ECG) parameters, EPS scales, the C-SSRS and the YMRS. For each safety parameter, the last assessment made before the first dose of double-blind investigational product will be used as the baseline for all analyses of that safety parameter. The summarization will be by treatment group for both double-blind and safety follow-up periods. Continuous variables will be summarized by number of participants and mean, SD, median, minimum, and maximum values. Categorical variables will be summarized by number and percentage of participants.

10.1 **ADVERSE EVENTS**

Adverse events will be coded by system organ class and preferred term using the *Medical Dictionary for Regulatory Activities*, version 24.0.

An adverse event (AE) will be considered a treatment-emergent adverse event (TEAE) if the AE began or worsened (increased in severity or became serious) on or after the first dose of DB investigational product. Per case report form instructions, a new AE record will be created with a new AE onset date for any AE that worsens. Therefore, TEAEs can simply be identified as those AEs with recorded onset date (and time, if known) on or after the date of the first dose of study intervention.

An AE will be considered a TESAE if it is a TEAE that additionally meets any SAE criterion.

For the DB treatment period, the number and percentage of participants reporting TEAEs in each treatment group will be tabulated by system organ class and preferred term; by system organ class, preferred term, and severity; and by system organ class, preferred term, and relationship to the IP. If more than 1 AE is coded to the same preferred term for the same participant, the participant will be counted only once for that preferred term using the most severe and most related occurrence for the summarization by severity and by relationship to the IP.

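### No planned C-SSRS summary relates double-blind suicidal ideation to ideation just before treatment, so persisting ideation is counted together with new or worsened ideation

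*SAP*

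**What the plan says.** SAP 10.5.3, which repeats Protocol 7.3.3.5, specifies three C-SSRS outputs besides a listing of adverse events in affected patients:

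- A count by arm: "The number and percentage of patients with suicidal ideation or suicidal behavior as recorded on the C-SSRS will be summarized by treatment group".
- Distributions of the most severe ideation and behavior categories "during the patient's lifetime, during the DB treatment period, and during the safety follow-up period will also be presented by treatment group".
- Listings: "Supportive listings will be provided and will include the patient identification number, study center number, lifetime history, and postbaseline values". The Visit 2 rating is not named.

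SAP section 10.0 includes the C-SSRS among the safety parameters and sets a general rule: "For each safety parameter, the last assessment made before the first dose of double-blind investigational product will be used as the baseline". It also says: "The summarization will be by treatment group for both double-blind and safety follow-up periods".

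Protocol 6.6.6.2 supplies pre-treatment data. At Visit 1 the scale covers "lifetime history of suicidal ideation and behavior, including a 12-month lookback". At every later visit, including Visit 2 before dosing, it covers the interval since the previous visit.

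Protocol 4.4, criterion 6, excludes on suicide risk by threshold. One limb reads "Patient had a score of 4 or greater on Item 10 of the MADRS at Visit 1" (Visit 2 is included as well). The others are HAMD-17 item 3 of 3 or more, an attempt in the past year, and significant risk in the investigator's judgment.

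**The concern.** Ideation is a symptom of the disease under study and can be present at entry below the exclusion thresholds. A patient whose mild ideation continues unchanged then adds one to the double-blind count, as does a patient who first develops ideation on study drug. Lifetime history does not separate them, because it does not show status at randomisation. Distributions reported period by period do not show change within a patient.

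The safety question is whether adding cariprazine brings on or worsens suicidal ideation. The planned table answers a different one: how many patients in each arm had any ideation during treatment.

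**Working it through.** **Step 1. Can ideation be present at baseline?** Yes. MADRS item 10 below 4 and HAMD-17 item 3 below 3 are allowed, provided there was no attempt in the past year and the investigator does not judge the risk significant.

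**Step 2. Does any C-SSRS output use the pre-treatment rating?**

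- The n (%) table has no baseline condition in numerator or denominator.
- The severity distributions are separate by period, with no cross-tabulation.
- The listings pair lifetime history with postbaseline values.
- The section 10.0 baseline rule covers the C-SSRS, but nothing in 10.5.3 applies it.

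By comparison, treatment-emergent parkinsonism and akathisia (SAP 10.5.2) and potentially clinically significant laboratory and ECG values (SAP 10.2, 10.4) all require a non-case baseline.

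**Step 3. Is behavior affected in the same way?** Hardly. Behavior consists of discrete acts rated since the previous visit, so a double-blind record is normally a new event. Ideation is rated over the same intervals but can simply continue from one to the next.

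**Step 4. How large could the mixing be?** The plan has no figure to reproduce, and every rate below is an assumption. Let b be the proportion with baseline ideation, s = 60% the proportion of those still reporting it on treatment (equal in both arms), and e the new-onset rate among the rest.

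- Planned count: p = b × s + (1 − b) × e
- Persisting share of that count: b × s / p

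For b = 10% and e = 2% (placebo) versus 6% (active):

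- Placebo: 0.10 × 0.60 + 0.90 × 0.02 = 0.078
- Active: 0.10 × 0.60 + 0.90 × 0.06 = 0.114
- Ratio: 0.114 / 0.078 = 1.46, against an emergent ratio of 3.0
- Persisting share, placebo: 0.060 / 0.078 = 77%

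| b | Planned count, e = 2% vs 6% | Ratio (emergent 3.0) | Persisting, placebo | Planned count, e = 4% vs 8% | Ratio (emergent 2.0) | Persisting, placebo |
|---|---|---|---|---|---|---|
| 5% | 4.9% vs 8.7% | 1.78 | 61% | 6.8% vs 10.6% | 1.56 | 44% |
| 10% | 7.8% vs 11.4% | 1.46 | 77% | 9.6% vs 13.2% | 1.38 | 62.5% |
| 20% | 13.6% vs 16.8% | 1.24 | 88% | 15.2% vs 18.4% | 1.21 | 79% |
| 30% | 19.4% vs 22.2% | 1.14 | 93% | 20.8% vs 23.6% | 1.13 | 87% |

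The loss is in the relative contrast and in readability. With all patients as denominator, new onset alone at b = 10% is 0.90 × 2% = 1.8% versus 0.90 × 6% = 5.4%. The difference is 3.6 points, the same as 11.4% − 7.8%. At 250 per arm that is 4.5 versus 13.5 expected new cases, which the planned table shows as 19.5 versus 28.5 because 15 persisting cases are added to each arm.

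The model counts new onset only. The fix also counts worsening, so these figures illustrate the mixing and do not predict what the added tables would show.

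**The case against.** Much of the case on the other side stands.

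- **Emergent suicidality has other routes.** A reader might infer that it is never reported. The documents do not support that. Suicidality recorded as an adverse event enters the TEAE, TESAE and discontinuation outputs (SAP 10.1), and adverse events in patients with C-SSRS ideation or behavior are listed. SAP 9.3 also analyses change from baseline in each MADRS item, including suicidality, at Weeks 1, 2, 4 and 6. Neither route fills the gap. Protocol 9.1.1 keeps worsening of symptoms that are collected as efficacy variables out of adverse event reporting when it is unequivocally attributed to progression or lack of efficacy and is no greater than anticipated. Suicidality is rated on both the MADRS and the HAMD-17. A mean item change can also hide a few patients who worsen.
- **The C-SSRS is not the only measure without a baseline condition.** Treatment-emergent mania (SAP 10.5.1) and orthostatic hypotension (SAP 10.3) have none either. For mania, entry with a YMRS of 12 or more is excluded, so reaching 16 is a change in any case.
- **Randomisation protects the comparison.** Baseline ideation is balanced in expectation. Persistence dilutes the contrast and does not bias it, so a reading that the arm comparison is invalid would be wrong.
- **Severity is shown.** The most-severe-category distributions separate mild from severe ideation. They still do not show who changed.
- **The illustration rests on assumed rates.** Safety data are summarised descriptively and no C-SSRS test is planned, so power is not a relevant measure and none is claimed.
- **Output specifications are in a separate document** (SAP 3.0), which might already contain a shift table. The SAP does not call for one.

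**Conclusion.** The point holds for ideation. Neither document plans a C-SSRS summary that sets double-blind ideation against the patient's pre-treatment rating, although the ratings are collected and a baseline rule for the scale exists. The consequence is dilution. Under the assumed rates, emergent ratios of 2.0 to 3.0 appear as 1.13 to 1.78, and 44% to 93% of placebo patients counted are persisting cases. These ranges depend on baseline ideation of 5% to 30%, equal 60% persistence in both arms, and the two pairs of new-onset rates. If few patients enter with ideation, the effect is small.

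The point does not extend to suicidal behavior. It also does not show a biased comparison, or that emergent suicidality goes wholly unreported. It is a gap in a descriptive safety output that should be closed because the remedy is cheap and the question matters for this drug and population.

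**What to change.** In SAP 10.5.3, keep the existing tables and add by arm:

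1. A shift table from baseline C-SSRS ideation category (Visit 2, following the section 10.0 baseline rule) to the worst double-blind category.
2. The number and percentage with new or worsened ideation relative to that baseline, among participants with a baseline and at least one postbaseline C-SSRS.
3. As a supplementary view, the same summary against the worst category from the Visit 1 12-month lookback and Visit 2 combined.
4. The Visit 2 value in the listings.

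The two baselines have opposite weaknesses. Visit 2 covers only the screening interval, up to 14 days (21 with approval), so intermittent ideation can look new over six weeks of treatment. The 12-month worst case would miss a patient who was free of ideation at Visit 2 and had ideation return on treatment at an equal or milder level. The Visit 2 version should lead because it follows the SAP's own rule.

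The cost is SAP wording and two or three more descriptive tables. No new data and no change to study conduct are needed.

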15.0 DATA HANDLING CONVENTIONS

15.1 VISIT TIME WINDOWS

Table 15-1 presents the visits assigned for efficacy and safety analyses and the corresponding range of treatment days (window) during which an actual visit may occur.

Table 15-1 Efficacy and Safety Analysis Visit Definitions

Analysis Phase	Derived Visit	Scheduled Visit Day ^a	Window
Pretreatment	Baseline	Day 1	Days ≤ 1
Double-blind Treatment	Week 1	Day 8	Days [2, 11]
	Week 2	Day 15	Days [12, 21]
	Week 4	Day 29	Days [22, 35]
	Week 6	Day 43	Days ≥ 36 and within Double-blind Treatment Period
	End of Double-Blind Treatment Period ^b	Final double-blind treatment visit (expected Day 43) or ET visit during the double-blind treatment period	Final non-missing assessment during the double-blind treatment period
Safety Follow-up	Week 10	Day 71	day of final double-blind or ET visit during the double-blind treatment period $+1 \leq \text{Days} \leq \text{last visit}$

a Relative to the date of the first dose of double-blind investigational product. Day 1 = the date of the first dose of double-blind investigational product.

b Presented in analysis tables for safety parameters, including but not limited to electrocardiograms, clinical laboratory values, and vital signs.

ET = early termination.

If the visit date is on or after the date of the first dose of double-blind investigational product, the study day is calculated by visit date – date of the first dose of double-blind investigational product + 1. If the visit date is before the date of the first dose of double-blind investigational product, the study day is calculated by visit date – date of the first dose of double-blind investigational product. Therefore, a negative day indicates a day before the start of the double-blind investigational product.

If a participant has 2 or more visits within the same window, the last visit with a non-missing value will be used for analysis.

15.2 DERIVED VARIABLES

Some efficacy, safety variables and SF-12 health outcome measure are derived as follows:

- MADRS total score is the sum of the 10 items from the MADRS. If more than 2 items of MADRS are missing, then the total score will be set to missing
- HAMD-17 total score is the sum of the first 17 items from the 24-item Hamilton Depression Rating (HAMD) scale. If more than 2 items of the first 17 items of HAMD scale are missing, then the score will be set to missing
- HAM-A total score is the sum of all the 14 items from the HAM-A. If more than 2 items of the HAM-A are missing, then the total score will be set to missing
- YMRS total score is the sum of the 11 items of the YMRS. If more than 1 item of the YMRS are missing, then the total score will be set to missing.
- AIMS total score is the sum of the first 7 items of the AIMS. If more than 1 item for the AIMS (items 1-7) is missing, then the total score will be set to missing. Items 8 through 12 will be summarized separately
- SAS total score is the sum of the 10 items of the SAS. If more than 1 item for the SAS is missing, then the total score will be set to missing
- BARS total score is the sum of the first 3 items of the BARS. If any item for the BARS (items 1-3) is missing, then the total score will be set to missing. Item 4 will be summarized separately
- MADRS responders are defined as participants with a $\geq 50\%$ reduction from baseline in MADRS total score. The value is 1 for MADRS responders and 0 otherwise
- MADRS remission is defined as a MADRS total score of ≤ 10 . The value is 1 for MADRS remission and 0 otherwise
- CGI-I responders are defined as participants with a CGI-I score ≤ 2 . The value is 1 for CGI-I responders and 0 otherwise
- PCS-12 and MCS-12 derivation are described in the Section [15.2.1](#).

The total score for a specific variable at a particular visit will be calculated using (sum of non-missing items) × (total number of items) / (number of non-missing items) only if the number of missing items is less than the specified number for this safety variable. Otherwise, the total score will be set to missing. For the LOCF analysis, if a participant misses a postbaseline visit or if the postbaseline visit occurs outside the visit time window, a record for the scheduled visit will be imputed using the last non-missing value immediately before the missing value. If the missing value occurs at Week 1, the baseline value will be carried forward for Week 1, provided that at least 1 subsequent postbaseline assessment is available. For a composite scale such as MADRS total score, individual items of a rating scale will not be carried forward. Only total scores will be carried forward using the last-observation-carried-forward approach.

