6.6.6.1 Extrapyramidal Symptoms Scales

The following 3 scales will be used to systematically assess extrapyramidal side effects at Visits 2, 3, 4, 5, 6, or at ET.

Abnormal Involuntary Movement Scale

The AIMS ([Guy 1976](#)) assesses abnormal involuntary movements, such as tardive dyskinesia, associated with antipsychotic drugs; it measures facial, oral, extremities, and trunk movements, as well as the patient's awareness of abnormal movements. The first 10 items are rated on a none (0) to severe (4) scale. There are an additional 2 items on dental status that are answered yes or no.

Barnes Akathisia Rating Scale

The BARS ([Barnes 1989](#)) is a 4-item rating scale used to assess drug-induced akathisia. The scale comprises 3 items for rating the observable restless movements that characterize the condition, the subjective awareness of restlessness, and any distress associated with the akathisia (each on a 4-point scale from normal [0] to severe [3]). In addition, there is a global severity for akathisia item rated on a 6-point scale (absent [0] to severe akathisia [5]).

Simpson-Angus Scale

The SAS ([Simpson and Angus, 1970](#)) is a 10-item rating scale for assessment of antipsychotic-induced parkinsonism in both clinical practice and research settings. Each item ranges from 0 (normal) to 4 (extreme symptoms). The scale consists of 1 item measuring gait (hypokinesia), 6 items measuring rigidity, and 3 items measuring glabella tap, tremor, and salivation, respectively.

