12.2.4 Remote Assessment of Safety

For safety assessments that are conducted remotely (eg, by telephone, telemedicine virtual visit, video call), the following assessments are required to be completed in the course of the remote visit. **Note:** The source documents and eCRF (as applicable) should clearly denote which assessments have been completed remotely.

- Adverse Events/Serious Adverse Event Assessment
- Concomitant medication assessment
- Columbia-Suicide Severity Rating Scale (C-SSRS) - Must be conducted by a certified rater. Every effort should be made to have patients assessed by the same rater at each scheduled timepoint. In the event the rater certified for this study is unavailable, a rater certified on the C-SSRS for another Allergan trial may conduct the assessment.
- Young Mania Rating Scale (YMRS)
- Movement scales (BARS/AIMS/SAS) – Must be conducted by a certified rater. Telemedicine virtual visits (where available) or video calls (without recording) are the preferred method of remote assessment. If a scale item cannot be assessed, the item may be skipped and the source should indicate the item could not be assessed. Every effort should be made to have patients assessed by the same rater at each scheduled timepoint.

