- ^c If visit is being performed remotely, this assessment may be omitted at this timepoint. Patient should have this assessment performed as an Unscheduled assessment during the Safety Follow-up period. Clinical findings upon termination must be followed until the condition returns to prestudy status or can be explained as unrelated to investigational product. If necessary, an additional follow-up visit should be scheduled.
- ^d If visit is being performed remotely, study staff should verbally administer the Short-Form 12 (SF-12) to the patient and record the patient's responses in the source.
- ^e Movement scales may be conducted remotely if needed. Where possible, telemedicine virtual visits or video calls (without recording) should be used to conduct this assessment remotely. If a scale item cannot be assessed, the item may be skipped and the source should indicate the item could not be assessed. Movement scales may only be conducted by raters certified on the scale.
- ^f C-SSRS may be assessed remotely if needed by a certified rater. Clinicians with a valid C-SSRS certification for another Allergan study may rate C-SSRS in the event the study-certified rater is unavailable to complete the assessment.
- ^g As an alternative to in-person drug dispensing, IP may be dispensed via a secure delivery method (where permissible by local, statutory, federal/country law) and after approval by Sponsor.
- ^h Assessment of compliance should be performed at each visit. For remote visits where a pill count by site staff may not be possible, patient reported compliance is to be documented. Patient reported verification of IP capsules remaining should be documented.
- ⁱ To minimize undue burden on the patient, IP return may be less frequent during the time that visits are being conducted remotely but should occur no less frequently than monthly.
- ^j If visit is being performed remotely or at an alternate laboratory facility, this assessment may be omitted. In consideration of the processing time required, pharmacokinetic samples should not be collected during in-home visits.
- ^k Pharmacogenetic consent may be obtained at any time between Visit 1(Screening) and Visit 6 (Week 6). Pharmacogenetic consent may not be obtained remotely.

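### At COVID-19 remote visits, a SAS or BARS assessment whose rated items already exceed the cutoff can be set to missing, so it cannot count toward treatment-emergent parkinsonism or akathisia

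*SAP*

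**What the plan says.** - **Skipping items.** Protocol section 12.2.4, on remote safety assessment, says of the movement scales: "If a scale item cannot be assessed, the item may be skipped and the source should indicate the item could not be assessed". The COVID-19 visit schedule (Protocol Table 4, footnote e) repeats this: "Movement scales may be conducted remotely if needed". Neither place caps the number of skipped items or says which may be skipped. Under Protocol section 12.2 this applies only to randomized patients who have completed Visit 2.
- **Scoring.** SAP section 15.2: "SAS total score is the sum of the 10 items of the SAS", and "If more than 1 item for the SAS is missing, then the total score will be set to missing". For BARS the total is the sum of items 1 to 3, and any missing item among them voids it. A later paragraph of the same section prorates a total "only if the number of missing items is less than the specified number for this safety variable".
- **Case definition.** SAP section 10.5.2 defines treatment-emergent parkinsonism as a SAS score of at most "3 at baseline and > 3 at any DB assessment". Akathisia is defined in the same way on BARS, with a cutoff of 2. Counts and percentages by arm are promised. No denominator is given, and nothing is said about a missing total.
- **Item content.** Protocol section 6.6.6.1 scores SAS items 0 to 4 and the three summed BARS items 0 to 3. The SAS has "6 items measuring rigidity" among its 10 items.

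**The concern.** The definition asks only whether a threshold was crossed, and that can be known without a complete scale. The voiding rule suits a descriptive mean score, because a sum over few items is hard to compare with a full total. Applied to a threshold, it throws away visits at which crossing has already been shown.

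The error runs in one direction. The remote provisions start after Visit 2, so they affect post-baseline scores and leave the baseline condition alone. Voiding a post-baseline total can remove a case and can never create one. A patient missed in this way also drops out of the section 10.5.2 patient listings and the linked adverse event listings. Parkinsonism and akathisia are scale-based safety outcomes that the SAP chose to report by arm, and a loss of true cases shrinks the absolute difference between drug and placebo.

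**Working it through.** The documents state no rate or sample size for this outcome, so there is no figure of the plan to reproduce. The check applies the scoring rules directly.

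**1. SAS.** Let m be the number of skipped items and S the sum of the rated ones. Items score 0 to 4, so the full total lies between S and S + 4m. Under the more-than-one rule, the SAP total is S × 10 / (10 − m) for m of 0 or 1, and missing otherwise.

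| m | S | Possible full total | SAP total | Certainly > 3? |
|---|---|---|---|---|
| 0 | 4 | 4 | 4 | yes |
| 1 | 3 | 3 to 7 | 3 × 10/9 = 3.33 | no |
| 1 | 4 | 4 to 8 | 4 × 10/9 = 4.44 | yes |
| 2 | 4 | 4 to 12 | missing | yes |
| 2 | 6 | 6 to 14 | missing | yes |
| 6 | 4 | 4 to 28 | missing | yes |
| 6 | 16 | 16 to 40 | missing | yes |

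Once two items are skipped, no observed sum makes the visit count. The last row is the extreme: all six rigidity items skipped and the other four at their maximum (4 × 4 = 16).

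**2. BARS.** With one of the three items skipped and the other two rated 3 and 0, the total lies between 3 and 3 + 3 = 6. It exceeds 2 for certain, but the SAP total is missing.

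**3. Does another rule rescue the visit?** Proration stops at one missing SAS item. Carrying the last observation forward is described only for the LOCF analysis. SAP section 16.2 counts missed EPS-scale assessments but gives no rule for scoring a partial one.

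**4. Conflict within section 15.2.** One sentence voids SAS when more than one item is missing. The proration sentence requires fewer missing items than the specified number. With that number equal to one, a single missing item voids the total, and both m = 1 rows above become missing.

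**5. From visit to patient.** The definition is met at any double-blind assessment, and the scales are given at Visits 3, 4, 5 and 6/ET. Suppose a patient is truly above the cutoff at v visits and each of these is voided with probability r, independently. The patient is lost with probability r^v. Taking r from 5% to 50% as an assumption:

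- v = 1: 5% to 50% of such patients lost; a true 10% would appear as 9.5% to 5.0%.
- v = 2: 0.05² = 0.25% to 0.5² = 25% lost.
- v = 4: almost none to 0.5⁴ = 6.25% lost.

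The loss is larger if one patient's visits are all remote. It is also an upper limit on what can be recovered, because a voided visit is provably above the cutoff only if its rated items alone exceed it.

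**6. Denominator.** Suppose 50 patients have only visits with all rigidity items skipped, and 3 of them have a rated sum above 3. Nobody can be ruled out. A denominator limited to classifiable patients gives 3/3. Keeping all 50 gives 3/50 = 6%, with 47 undetermined.

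**The case against.** The strongest reply is that the gap is narrow and its frequency unknown. It concerns visits affected by COVID-19 only. Home visits allow examination, and video is the preferred remote method for the movement scales. One scorable visit above the cutoff still makes the patient a case. EPS adverse events, with a parkinsonism cluster and akathisia, are tabulated under SAP section 10.1 without reference to these totals, and rescue medication for EPS is summarized as well. For BARS, subjective awareness and distress can be obtained by interview, so skipping should be rarer. All of this stands and limits the size. It does not make the rule right for a visit at which the cutoff has demonstrably been exceeded.

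Three stronger readings are tempting, and the documents do not support them.

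- A reader might infer that these patients are counted as non-cases. The case does leave the numerator, but section 10.5.2 gives no denominator, and table specifications sit in a separate document (SAP section 3.0). With the safety population as denominator, the default in section 10.0, they would be non-cases. If a computable post-baseline total were required, a patient with no scorable visit would be left out instead.
- A reader might infer that rigidity cannot be rated by telephone or video, so that several items will routinely be skipped. That is plausible, but neither document says so.
- A reader might infer that if 10% to 20% of patients have no computable SAS, rates fall by the same share, for instance from 8% versus 3% to 7.2% versus 2.7% or 6.4% versus 2.4%. All of these inputs are assumptions. The sum also removes every case among such patients, although only those whose rated items exceed the cutoff are provably lost. The ratio stays at 2.67 throughout (8/3 = 7.2/2.7 = 6.4/2.4); only the absolute difference shrinks.

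**Conclusion.** The point holds for individual visits. A remote visit with two or more SAS items skipped and a rated sum above 3, or with a BARS item skipped and a rated sum above 2, is proven to exceed the cutoff, yet the stated rule discards it. That conclusion needs only the item ranges. The patient is missed unless another scorable double-blind visit exceeds the cutoff. Voiding can only reduce the number of cases, and with a fixed denominator it can only lower the scale-based rates.

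The size cannot be obtained from the documents. It depends on how many visits were remote and partly rated, which items were skipped, and how often a patient was above the cutoff. The range in the working rests on an assumed voiding probability and independent visits. This is a minor point, worth correcting because the correction is cheap.

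**What to change.** In SAP section 10.5.2:

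1. For patients with a qualifying baseline score, classify a post-baseline visit as above the cutoff when the sum of the rated items alone exceeds it (SAS > 3; BARS items 1 to 3 > 2). Leave the total missing for the descriptive score summaries.
2. State the denominator: safety-population patients with a qualifying baseline and at least one post-baseline assessment of the scale, full or partial. Do not limit it to patients who can be classified. Those with only partial visits would then enter chiefly when they are cases, and the rate would be inflated.
3. Report by arm the number of patients whose only post-baseline assessments are partial and at or below the cutoff, as status undetermined.

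In section 15.2, reconcile the two missing-item rules, so that it is clear whether one missing SAS item leads to a prorated or a missing total.

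The cost is a derivation change and one extra table row. No new data are needed, and no efficacy analysis changes. The downside is that a partial visit can confirm a case but cannot rule one out, so the rate remains a lower bound as far as voided visits are concerned. Proration of a single missing item is a separate matter: it can put a rated sum of 3 above the cutoff (3.33) when the full total might be 3.
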